Our **primary objective** is to determine the preliminary efficacy of the intervention. **Methods:** We will conduct a **two-group cluster randomized controlled trial** (RCT). From the available 13 large Head Start centers, six centers will be randomly selected and then randomly assigned to the intervention (n=3) or control group (n=3, usual Head Start activities); 24 caregiver-preschooler dyads will be recruited from each center (N=144 dyads).

AIM 1: Determine the preliminary efficacy of *FirstStep2Health* vs control among preschoolers on proximal behavioral changes of ↑ moderate-to-vigorous PA (MVPA) measured by accelerometry (primary outcome), ↑ diet quality (e.g., ↑ fruits/vegetables, ↑ fiber, ↑ whole grains, ↑ total protein, ↑ dairy, ↓ sugar-sweetened beverages, ↓ total sugars/fats), and ↓ screen time (e.g., watching TV, playing video games); and distal anthropometric outcomes of ↓ proportion of OW/O and ↓ body mass index (BMI) z-score. We anticipate an overall decrease in BMI z-score in intervention preschoolers because we expect OW/O preschoolers’ BMI z-score to decrease and healthy-weight preschoolers to have no change. We focus on proximal behavioral changes as our primary outcome instead of distal anthropometric outcomes due to the brevity of this study and the need for behavioral changes to be maintained for at least a year before manifesting in changes in anthropometric outcomes.^{49,50} **AIM 2: Examine the preliminary efficacy of *FirstStep2Health* vs control among caregivers** on their ↑ MVPA measured by accelerometry, ↑ diet quality (e.g., ↑fruits/vegetables, ↑fiber), ↓ screen time, ↓ proportion of OW/O, ↓ BMI, ↑ knowledge, ↑ feeding practice skill, ↑ self-efficacy, ↑ parental support of their child, ↑ parenting practices, and ↑ home environment. **AIM 3: Compare *FirstStep2Health* vs control on the bidirectional relationship** (as demonstrated in the APIM) between preschoolers and caregivers on MVPA, diet quality, and screen time. Further, we will **validate established feasibility, acceptability, and satisfaction of the intervention using qualitative and quantitative data**.

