C.5. SETTING & SAMPLE. Six Head Start centers (≥ 4 classes/center) will be randomly selected from the Capital Area Community Services (CACs) Head Start and Early Childhood Programs and the Head Start for Kent County, which had 13 centers with ≥ 4 classes in 2017.^{126,127} Among the 13 centers, two had 4, one had 5, five had 6, one had 8, one had 9, two had 12, and one had 14 classes. The 13 centers cared for 1,932 preschoolers: 49% female, 20% Hispanic, 38% Black, and 39% White. Four classes will be randomly selected from each center, and 6 caregiver-preschooler dyads will be randomly selected from the eligible participants in each class (total: 6 centers, 24 classes, and 144 dyads). Inclusion and exclusion criteria are specified in **Table 1**.

C.6. SAMPLE SIZE & POWER. Due to the exploratory/developmental focus of this R21 grant proposal, our aim is to estimate effect sizes for proximal and distal outcomes in preschoolers to serve as foundation for future research. Assuming class cluster effects intraclass correlation (ICC)=0.01,^{128,129} and

significance level=.05, a sample size of 130 will provide a power of .80 to identify an effect size of 0.50, < 0.66 for MVPA achieved in the prior study after adjusting for demographics.³⁸ Given the extended intervention duration from 10 to 16 weeks and the strengthened intervention, we anticipate to also achieve an effect size of 0.50 in preschoolers' diet quality, screen time, and BMI z-score. We conservatively assume a 10% dropout.

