Head Start center environment, including the physical environment, provisions, practices, policies, training, and education. All other surveys will be completed by caregivers online via REDCap web application. Caregivers will be informed of online surveys via text-message or email. Data collectors and interviewers (blinded to group assignment) will be available by phone or in-person to answer questions.

Table 5. Study Measures

Concept	Measure and Description	# Items	Time	Reliability/Validity
Preschoolers (Aim 1)				
MVPA (min/day)	7-day ActiGraph GT3X-plus accelerometer ¹⁴⁵ Cut-points: sedentary activity (<37 counts/15 s), light (38–419), moderate (420–841), & vigorous (≥842) ^{146,147}	7-day	5 min	Reliability = 0.69–0.84 ¹⁴⁸ $r = 0.66$ with observational system ¹⁴⁵
Diet quality (e.g., fruit/vegetable, fiber, sugar/fat)	Intake at Head Start center: dietary observation system on snacks and lunch on two weekdays ¹⁴⁹ Intake at home: proxy-reported 24-hour dietary recall	3-day	90 min	ICC = 0.99; ¹⁴⁹ accurate rate: 95%; ¹⁵⁰ good agreement with actual energy intake ¹⁵¹
Screen Time	NHANES-Physical Activity and Physical Fitness survey ¹⁵²	2	1 min	Reliability: $r = 0.63–0.84$ ¹⁵³
Proportion of OW/O, BMI z-score	Calculated from height and weight using CDC growth charts ¹⁵⁴ Height: Child/Adult Shorr Measuring Board Stadiometer Weight: Child/Adult Seca model 874 portable electronic scale In accordance with NHANES measurement protocol ¹⁵⁵	N/A	3 min	Specificity 0.93; sensitivity 0.73 ¹⁵⁶
Caregivers (Aim 2)				
MVPA	7-day ActiGraph GT3X-plus accelerometer Cut-points: light (0–2689 counts/60 s), moderate (2690–6166), & vigorous (≥6167) ¹⁵⁷	7-day	5 min	ICC = 0.97–0.99 ¹⁵⁸ $r = 0.81$ with oxygen consumption ¹⁵⁹
Diet quality	Fruit-vegetable-fiber screener ¹⁶⁰	10	3 min	$r = 0.71$ with full Block survey ¹⁶⁰
Screen Time	NHANES-Physical Activity and Physical Fitness survey ¹⁵²	2	1 min	Reliability: $r = 0.63–0.84$ ¹⁵³
Proportion of OW/O, BMI	Calculated using (weight kg/height m^2) ¹⁶¹ Measures are similar to those used in preschoolers	N/A	3 min	Specificity 0.97; sensitivity 0.42 ¹⁶²
Knowledge	Knowledge on preschoolers' dietary intake & physical activity ¹⁶³	25	5 min	N/A
Feeding Practice Skill	Child Feeding Questionnaire ¹⁶⁴ measuring caregiver feeding practice behaviors	33	5 min	$\alpha = 0.71–0.93$ ^{38,164,165} $r = -0.26–0.53$ with child BMI ^{164–166}
Self-Efficacy	Parental self-efficacy scale ¹⁶³	20	4 min	$\alpha = 0.72–0.94$ ^{38,163}

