Parental Support	Parental support scale for eating habits and physical activity ¹⁶⁷	12	3 min	$\alpha = 0.83–0.87$ ^{38,167,168}
Parenting Practices	Parenting Style and Dimensions Questionnaire ¹⁶⁹ assessing parenting styles: authoritative, authoritarian, and permissive	32	5 min	$\alpha = 0.64–0.91$ ¹⁷⁰
Home Environment	Family Nutrition and Physical Activity (FNPA) screening tool ¹⁷¹ assessing home obesogenic environments and practices	20	4 min	Correlated with child BMI ^{171,172}
Demographics	Socio-demographic questionnaire (e.g., age, sex, race)	12	3 min	N/A
Center Environment	EPAO-SR ¹⁴⁴	1-day	30 min	Related to observational data ¹⁴⁴

C.15. DATA ANALYSIS. Any missing at random (MAR) data will be imputed using procedures suggested by Potthoff.¹⁷³ For non-MAR data, a sensitivity analysis will be performed following recommended approaches for continuous and discrete outcomes.^{174–177} All analyses will use the intention-to-treat¹⁷⁸ principle. Data analysis will be disaggregated by sex in preschoolers. **AIM 1 & 2:** Mixed-effect models in SAS 9.4 will be used to evaluate the intervention efficacy. Fixed effect predictors will include group, time, groupXtime interaction, and potential confounders such as preschooler sex, race, baseline weight status, and caregiver marital status. The correlation of preschooler outcomes measured over time and dependence due to nesting in the same center or class will be accounted through center- and class-specific random cluster effect. Contrasts will quantify the intervention effects separately at the post-intervention. Holm's method will be used to statistically control for multiple comparisons.¹⁷⁹ Effect size (Cohen's d) will be calculated. **AIM 3:** Path analysis will be conducted using EQS 6.2. Model fit will be assessed using root mean square error approximation, Normed Fit Index, and Tucker Lewis index. Chi-square difference test¹⁸⁰ will be used to compare models. Model modification will be made if needed. Feasibility/acceptability/satisfaction will be determined through enrollment, intervention participation, and evaluation survey data. Recorded individual interviews will be analyzed using directed content analysis in ATLAS.ti 8 to evaluate reasons for satisfaction and suggestions for improvement.

Table 6. Method Considerations

Issue	Justification and Strategies

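### C.15 gives the over-time correlation of preschooler outcomes to center and class random effects, which cannot carry it, so the reported standard errors would be wrong: modestly at week 17, more for group-by-time

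*Combined protocol and SAP*

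**What the plan says.** C.15 (Data Analysis, Aims 1 and 2) specifies mixed-effect models in SAS. On the fixed part it says "Fixed effect predictors will include group, time, groupXtime interaction", plus potential confounders. On the covariance it has one sentence, about preschooler outcomes, which says that their correlation "measured over time and dependence due to nesting in the same center or class will be accounted through center- and class-specific random cluster effect". On the estimate it says "Contrasts will quantify the intervention effects separately at the post-intervention". It states no degrees of freedom.

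C.4 gives two measurement occasions, week 0 and week 17. C.5 gives 6 centers, 24 classes and 144 dyads, and the centers are randomized 3 to 3. C.6 says "our aim is to estimate effect sizes for proximal and distal outcomes in preschoolers".

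No other section names a participant random effect, a repeated-measures structure or a within-child covariance. The sentence speaks of preschooler outcomes only. No covariance structure is given for caregiver outcomes, although the paragraph covers both aims.

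**The concern.** The sentence gives the center and class effects two jobs, and they can do only one. Given those effects, the model treats a child's two measurements as no more alike than that child's baseline and a classmate's week-17 value. Using the class intraclass correlation (ICC) of 0.01 in C.6, the implied within-child correlation is about 0.01.

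Two errors follow, in opposite directions. Ignoring the child-level correlation puts stable differences between children into the residual, which makes the SE of a change too large. If the center effects are constant over time, variation between centers in change is also left out. Centers are the randomized units, so this makes the SE too small.

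The trial's stated product is a set of effect sizes for planning later research, and its primary outcome, preschooler MVPA, goes through this model. If the precision attached to those estimates is wrong in a direction that a reader cannot determine, they are less useful for planning.

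**Working it through.** **C.6 first.** C.6 says "Assuming class cluster effects intraclass correlation (ICC)=0.01" and "a sample size of 130 will provide a power of .80 to identify an effect size of 0.50". For d = 0.50, two-sided .05 (sidedness assumed) and power .80, n = 63 per arm, or 126 in total. The class design effect with 6 per class is 1 + 5 × 0.01 = 1.05, so N = 126 × 1.05 = 132.3. Power at N = 130 is .794. The stated figure therefore reproduces on its own basis: one time point, class ICC, large df. It does not use the C.15 model.

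**Inputs.** From the documents: 6 centers × 4 classes × 6 children × 2 occasions. Assumed: total variance 1; center and class variance 0.01 each; center-by-time variance v = 0, 0.01, 0.02 or 0.05; over-time correlation rho = 0.3, 0.5 or 0.7, with child variance ch = rho × (0.98 − v) and error variance e = (1 − rho) × (0.98 − v). Covariates are not modelled; they would lower the residual rho.

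**True variances**
- Week 17: 2 × [(0.01 + v)/3 + 0.01/12 + (0.98 − v)/72]
- Group-by-time: 4v/3 + 4e/72

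**Residual variance under the as-written model.** It pools 120 df between children within class, 142 df within children, and any center-by-time variation:

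s2 = [120 × (2ch + e) + 142e + 96v] / 262

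The reported group-by-time variance is 4 × s2/72.

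**Group-by-time, worked at rho 0.5**
- v = 0: ch = e = 0.49. s2 = (120 × 1.47 + 142 × 0.49)/262 = 0.939. Reported SE = √(4 × 0.939/72) = 0.228; true SE = √(4 × 0.49/72) = 0.165; ratio 1.38.
- v = 0.05: ch = e = 0.465. s2 = (167.40 + 66.03 + 4.80)/262 = 0.909. Reported SE = 0.225; true SE = √(0.0667 + 0.0258) = 0.304; ratio 0.74.

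**Week 17, worked at rho 0.5, v = 0.** The class term absorbs part of the child variance: 0.01 + (1.47 − 0.939)/12 = 0.054. Reported SE = √{2 × [0.01/3 + 0.054/12 + 0.939/72]} = 0.204; true SE = 0.189; ratio 1.08. This is without any bound on the variances. For rho 0.3 and 0.7 the same formula gives 1.05 and 1.12.

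**Simulation of the as-written fit** (REML with variances bounded at zero, 40,000 trials per setting). Each cell is reported/true SE, with type I error on a large-df cut-off in brackets.

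| Contrast | rho | v = 0 | v = 0.01 | v = 0.02 | v = 0.05 |
|---|---|---|---|---|---|
| Week 17 | 0.3 | 1.10 (.045) | 1.04 (.057) | 1.00 (.070) | 0.91 (.103) |
| Week 17 | 0.5 | 1.13 (.039) | 1.07 (.051) | 1.03 (.063) | 0.93 (.097) |
| Week 17 | 0.7 | 1.17 (.033) | 1.11 (.046) | 1.06 (.057) | 0.96 (.089) |
| Group-by-time | 0.3 | 1.18 (.023) | 1.02 (.047) | 0.90 (.078) | 0.71 (.170) |
| Group-by-time | 0.5 | 1.38 (.008) | 1.13 (.027) | 0.98 (.058) | 0.74 (.151) |
| Group-by-time | 0.7 | 1.77 (.001) | 1.31 (.011) | 1.09 (.034) | 0.78 (.128) |

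**Splitting the week-17 excess at v = 0.** The unbounded ratios are 1.05, 1.08 and 1.12, against 1.10, 1.13 and 1.17 with the bound. A bounded model that does contain a child effect still gives about 1.05, against 1.09-1.15 as written in the same runs. The missing child term therefore accounts for roughly 4-12%, and the bound for the rest.

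**Degrees of freedom.** On 6 − 2 = 4 df, the as-written tests reject a true null in .004-.027 of trials at week 17 and in at most about .05 for group-by-time.

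**A child effect alone is not a repair.** It makes the reported group-by-time variance 4 × (e + 96v/142)/72. At rho 0.5 and v = 0.01 this is 4 × (0.485 + 0.0068)/72, SE 0.165, against a true SE of 0.201: ratio 0.82.

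**The case against.** **The plan's own contrast is the less affected one.** C.15 quantifies effects at post-intervention, where the error is modest and part of it comes from bounding variances at zero. The large ratios belong to group-by-time, a listed fixed effect but not the stated contrast. This stands, and it limits the size of the point.

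**A reader might infer a false-positive problem.** The documents do not support that. Every type I rate above .05 in the table depends on a large-df cut-off, and the plan names no df. On 4 df neither contrast shows material inflation.

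**The inputs are assumed.** This also stands. Neither rho nor the center-by-time variance is documented, and v = 0.05 is five times the only ICC given. It is tempting to read the MVPA entry in Table 5, "Reliability = 0.69–0.84", as a ceiling on rho. It is not a 17-week correlation, and the documents do not say that it bounds one, so it is context only.

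**The sentence may be compressed drafting.** It does not prove what was coded, and a repeated-measures term may have been intended. But none is written, and the sentence does more than stay silent: it gives the correlation to terms that cannot hold it. Either way the wording needs the same correction.

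**The trial is exploratory.** C.6 says so, and point estimates in the balanced layout do not change. That argues for a proportionate fix. It does not make the SE unimportant when effect-size estimation is the declared aim.

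**Conclusion.** The wording defect is certain: the stated covariance structure cannot represent the correlation between a child's two measurements, and nothing else in the plan supplies it. Fitted as written, the SE is wrong.

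- With cluster effects constant over time and rho 0.3-0.7, it is about 10-17% too large at week 17 under zero-bounded REML and about 18-77% too large for group-by-time.
- With center-by-time variance of 0.05, it falls to 0.91-0.96 of the truth at week 17 and 0.71-0.78 for group-by-time.

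Direction and size rest on the assumed rho and center-by-time variance, a balanced layout, a continuous outcome and no covariates. They were not worked out for the binary outcome behind "distal anthropometric outcomes of ↓ proportion of OW/O", where the same gap in wording applies.

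A reader might go on to conclude that the .80 in C.6 fails for this reason. It does not: that figure reproduces on its single-time-point, class-ICC basis. Whether it holds on center-level df is a separate question. The point should be fixed before analysis, but it does not undermine the design.

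**What to change.** Replace the covariance sentence so that the within-participant correlation is modelled explicitly.

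**Preferred, for continuous outcomes and the post-intervention contrast:** a week-17 model with the participant's baseline value and the planned covariates as fixed effects and random effects for center and class, with the group effect tested on 4 center-level df, set explicitly. The sentence listing time and group-by-time must then be amended as well. In balanced simulation, with variances not bounded at zero, type I error was .045-.054.

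**If the two-occasion model is kept:** add a participant random effect or an unstructured 2×2 within-participant covariance together with a center-by-time random effect, and test group-by-time on 4 df (simulated type I error .049-.052). The week-17 contrast from this model is conservative on 4 df (.024-.035), so it is not the better choice for the plan's contrast.

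Apply the same structure to caregiver outcomes, and say whether variances are bounded at zero.

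**Cost.** The change is wording and a few lines of SAS, with no new data. The downside is power. With 144 children, d = 0.50 and rho 0.5:

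| Test | v = 0 | v = 0.01 | v = 0.02 | v = 0.05 |
|---|---|---|---|---|
| As written, week 17, large df | .67 | .64 | .62 | .56 |
| Baseline covariate, 4 df | .70 | .58 | .48 | .34 |
| Two-occasion, group-by-time, 4 df | .63 | .47 | .38 | .25 |
| Two-occasion, week 17, 4 df | .51 | .43 | .38 | .27 |

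Over the settings examined, the baseline-covariate test beats the as-written week-17 test only at rho 0.5 with v = 0 and at rho 0.7 with v = 0 to 0.01. Where v is larger, the as-written power is partly bought with type I error above .05. The plan should state this loss openly.

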Suggestions. Fifteen randomly selected caregivers were interviewed individually. They suggested: **1)** holding each caregiver meeting on both weekday and weekend so working caregivers can attend; **2)** covering topics on alternative cooking ingredients and portion size control during the meeting; **3)** promoting more interactions via commenting on others' postings; **4)** including quick meal recipes and healthy snack ideas in the intervention cookbook; and **5)** extending the program a few more weeks. Results support the feasibility of the intervention, but preliminary efficacy needs further evaluation using a more rigorous design and larger sample size.

Fig 1. Actor-Partner Interdependence Model

C.3. CONCEPTUAL FRAMEWORK (Fig 1). The intervention is guided by an Actor-Partner Interdependence Model (APIM),⁴³ which has been used in behavioral interventions to better understand the intergenerational relationships inside a family.¹¹⁴⁻¹¹⁶ The APIM demonstrates the bidirectional relationship between preschoolers and caregivers: **1)** actor effects within preschoolers or caregivers, and **2)** partner effects between preschoolers and caregivers.⁴³ The proposed intervention targets both preschoolers' and caregivers' knowledge, skill, self-efficacy, and social support, derived from social cognitive theory,¹¹⁷ and parenting practices and home environment¹¹⁸⁻¹²³ to improve their MVPA, diet quality, and screen time, thereby reducing the proportion of OW/O and BMI. Participatory learning³⁴ will be used to improve preschoolers' knowledge, skill, self-efficacy, and social support, but will not be assessed due to preschoolers' immature cognitive development.¹²⁴ Caregivers' learning³⁴ will be improved via weekly habit-formation tasks on child feeding practices and PA and preschooler letters where preschoolers describe their desires for healthy diet and PA at home. Through simultaneously targeting both preschoolers and caregivers to maximize the actor and partner effects, the intervention is hypothesized to result in positive outcomes.

C.4. STUDY DESIGN. To decrease cross-group contamination among participants in the same location,¹²⁵ we will employ a rigorous two-group cluster RCT design by randomizing 6 centers so participants in one center are in the same group. Data will be collected at baseline (wk. 0) and immediately post-intervention (wk. 17).

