C.7. RECRUITMENT. The two Head Start organizations have agreed to support implementing the proposed project in their Head Start centers (**Support Letters**). Based on our prior experiences working with Head Start families, we anticipate ≥ 6 of 18 (30%) dyads per class will be willing to participate. Replacement classes will be randomly chosen if a selected class teacher refuses to participate. Building on lessons learned from prior studies and recommendations from Head Start administrators, we will involve Head Start family advocates to help with recruitment because they already have an established, trusting relationship with each family. The PI and project manager (PM) will provide participant recruitment training with communication scripts to family advocates to ensure consistency. Family advocates will distribute the recruitment packet (including cover letter, parental consent/child assent, & screening tool) in an envelope and explain the study to each caregiver in person. Each family will be asked to return the packet in a sealed envelope to the family advocate. For non-respondents, the family advocates will make a follow-up phone call, and then another packet will be mailed to each family. Each family will be asked to return the packet in an attached, prepaid envelope. Cash (\$5) will be provided for returning the packet. Prior to any data collection, written parental consent is required; if the child is age 5, written child assent is required. No data will be collected from preschoolers in the selected classes who do not have written consent or assent, but these preschoolers will be allowed to participate in intervention activities at their Head Start center. Both male and female preschoolers and caregivers will be recruited.

C.8. RANDOMIZATION AND BLINDING. Following baseline data collection, 6 randomly selected centers will be randomly assigned to intervention or control using a computerized random-number generator. Center directors and teachers will be informed of group assignment. There is no way to completely blind participants

Table 1. Inclusion and Exclusion Criteria

Preschoolers	Caregivers
Inclusion Criteria	
Parental written consent	Provide written consent
Understand and speak English	Read, understand, and speak English
3-5 years old	Primary adult caregiver (≥ 18 years old)
Enrolled in full-day or half-day Head Start program	Have at least weekly Internet access using a smartphone, tablet, or a computer

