C.13. INTERVENTION FIDELITY MONITORING & EVALUATION. The PM will monitor the Facebook group daily to record task-completion rates and caregivers' site visits, respond to caregivers' questions and postings, and review records and posted content to ensure proper posting and functionality. Extension health educators will record caregiver meeting attendance and activities, as well as each preschooler's attendance, punctuality, participation, and activities offered for the day in a daily activity log. The PI will communicate with Extension health educators weekly to review objectives, attendance, and intervention delivery dose, and discuss issues and solutions. Head Start teachers will complete an evaluation survey on preschooler program, and caregivers will complete an evaluation survey on caregiver program and preschooler letters (**Appendix A**). Two process evaluators will observe 6 randomly sampled sessions (2/center; 1 session from Extension health educator and 1 session from teacher) to evaluate preschooler curriculum implementation and activity engagement. At post-intervention, individual interviews (**Appendix A**) with 10 randomly selected caregivers will be conducted with the PM and PI to obtain in-depth evaluation of the intervention and future suggestions for improvement.

C.14. DATA COLLECTION & OUTCOME MEASURES (Table 5, Appendix A). All outcomes will be assessed at baseline and post-intervention. Height and weight will be measured in a private room in Head Start centers. To improve compliance with wearing accelerometers, an auto text-message reminder will be sent to caregivers every morning at 7AM via the *REDCap* web application maintained by MSU CTSI-BRIC (**Support Letter**). The 24-hour dietary recall will be administered by 4 trained interviewers via telephone¹⁴⁰ on 2 weekdays and 1 weekend day,^{141,142} using the Nutrition Data System for Research (NDSR) software developed by the Nutrition Coordinating Center,¹⁴³ University of Minnesota. Trained interviewers will also observe the snacks and lunch offered at Head Start centers. Drs. [name] & [name], who have completed the 2-day training on NDSR, will assess and assure diet data quality. The Environment and Policy Evaluation and Observation-Self-Report (EPAO-SR)¹⁴⁴ will be completed by each center supervisor and two teachers on a single day to assess each

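### C.15 names no adjustment for an outcome's own baseline value (child MVPA, diet, screen time, caregiver outcomes), which probably costs precision but introduces no bias

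*Combined protocol and SAP*

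**What the plan says.** The Aim 1 and 2 paragraph of C.15 specifies mixed-effect models: "Fixed effect predictors will include group, time, groupXtime interaction", together with "potential confounders such as preschooler sex, race, baseline weight status, and caregiver marital status". Clustering and correlation over time "will be accounted through center- and class-specific random cluster effect". The effect is then defined by "Contrasts will quantify the intervention effects separately at the post-intervention", and "Effect size (Cohen's d) will be calculated".

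The design supplies a pre-randomization value of every outcome. C.14 states "All outcomes will be assessed at baseline and post-intervention", and C.8 states "Following baseline data collection, 6 randomly selected centers will be randomly assigned to intervention or control". C.4 has two waves only, week 0 and week 17. Aim 1 makes accelerometer-measured child MVPA the primary outcome.

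The only baseline outcome measure named as a covariate is weight status. That partly serves child BMI z-score and overweight/obesity. Nothing equivalent is named for child MVPA, diet or screen time, or for the caregiver outcomes. No constraint of equal arm means at baseline is stated, and a group main effect is listed.

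**The concern.** Baseline is in the model, but only as the time-0 response. With free arm means at each wave and complete data, the week-17 arm difference is simply the difference in week-17 means, so the baseline values add no precision to it. If the contrast is instead the group-by-time term, baseline is used as an unweighted change score, with the slope fixed at 1 rather than estimated.

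C.6 says that the purpose is to estimate effect sizes on which later work will build. With six centers those estimates will be imprecise, and the data that could sharpen them are already being collected. C.15 also does not say outright which of the two contrasts is meant, and their variances can differ considerably.

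**Working it through.** **1. The plan's own figure.** Inputs from C.6: d = 0.50, significance level .05 (taken as two-sided), power .80, class ICC 0.01, 130 analysed. From C.5: 24 classes, so 130/24 = 5.42 children per class.
- n per arm = 2(1.960 + 0.842)²/0.50² = 62.8, rounded up to 63, or 126 in all.
- Design effect = 1 + (5.42 − 1)(0.01) = 1.044, and 126 × 1.044 = 131.6, so 132 against the stated 130. Power at 130 is 0.797.

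C.6 therefore reproduces with no baseline correlation in it.

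**2. Variance of the effect estimate.** Take k clusters per arm, n children per cluster, total SD 1, child-level correlation over time rw (written rho below) and cluster-level correlation over time rc:

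V(b) = (2/k)·[ICC(1 + b² − 2b·rc) + ((1 − ICC)/n)(1 + b² − 2b·rw)]

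Here b = 0 gives the week-17 contrast, b = 1 the change contrast and b = rw own-baseline adjustment. Rho is not in the documents, so 0.3 to 0.7 is assumed. C.6 gives its ICC of 0.01 for classes only, so two versions are run:
- class version: k = 12, n = 65/12, no center variance;
- center version: k = 3, n = 65/3, with 0.01 assumed for centers.

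rc runs from 0 to 1 in both.

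Example (center version, rho 0.5): (1 − 0.01)/n = 0.0457, so the week-17 bracket is 0.01 + 0.0457 = 0.0557.
- Adjusted, rc = 0: 0.01 × 1.25 + 0.0457 × 0.75 = 0.0468, ratio 0.840.
- Adjusted, rc = 1: 0.01 × 0.25 + 0.0457 × 0.75 = 0.0368, ratio 0.660.

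Ranges over both versions and all rc:

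| rho | adjusted / week-17 | adjusted / change | change / week-17 |
|---|---|---|---|
| 0.3 | 0.835–0.942 | 0.625–0.727 | 1.149–1.508 |
| 0.5 | 0.660–0.840 | 0.712–0.805 | 0.820–1.180 |
| 0.7 | 0.435–0.686 | 0.806–0.883 | 0.492–0.851 |

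When rc = rw, the last column is 2(1 − rho): 1.4, 1.0 and 0.6.

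**3. Equivalent sample size.** Solve for the n′ per cluster that gives the unadjusted week-17 contrast the adjusted variance: n′ = (1 − ICC)/(V·k/2 − ICC). Center version, rho 0.5, rc = 0: 0.99/(0.0468 − 0.01) = 26.9 per center, × 6 ≈ 162. With rc = 1: 0.99/(0.0368 − 0.01) = 37.0, × 6 ≈ 222. The class version lies inside this range (170 to 183). At rho 0.3 the range is about 140 to 163.

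**4. Interval width.** Center version, rho 0.5, 4 df (t = 2.776): the half-width is 0.535 SD for the week-17 contrast and 0.490, 0.463 and 0.435 SD after adjustment at rc = 0, 0.5 and 1.

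**5. When the gain disappears.** Write w = (1 − ICC)/n.
- The worst case against week 17 is rc = 0: the difference in brackets (adjusted minus week-17) is rw²(ICC − w).
- The worst case against change is rc = 1: the difference (adjusted minus change) is (1 − rw)²(ICC − w).

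Both are negative only if ICC < w, that is ICC < 1/(n + 1) = 1/22.67 = 0.044, whatever rho is. With the slope estimated, simulated worst-case ratios were 0.91–0.99 (week 17) and 0.89–0.96 (change) at center ICC 0.03, and 0.99–1.01 and 0.99–1.00 at 0.04.

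At center ICC 0.10 and rho 0.5, w = 0.0415:
- against week 17: (0.10 × 1.25 + 0.0415 × 0.75)/(0.10 + 0.0415) = 1.10;
- against change: (0.10 × 0.25 + 0.0415 × 0.75)/0.0415 = 1.35.

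**6. One trial rather than the average.** In 20,000 simulated trials with six centers of 22 children (center ICC 0.01, rho 0.5, SE estimated from center means), mean half-width fell from 0.50 to 0.407–0.458. The adjusted interval was nevertheless wider than the week-17 interval in 22.9% to 36.5% of trials.

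**7. Cohen's d.** C.15 names no SD. Dividing by the SD left after baseline adjustment multiplies d by 1/√(1 − rho²) = 1.05, 1.15 and 1.40 at rho 0.3, 0.5 and 0.7.

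**The case against.** The best defense is that nothing in C.15 is wrong. A two-wave group-by-time mixed model is a standard, valid analysis; baseline is already in it; and the covariates are introduced as examples, so own-baseline adjustment is unstated rather than ruled out. C.6 reproduces without any baseline correlation, so the trial keeps the precision it planned for. All of that stands. A reader might infer that the analysis is biased, that it discards baseline, or that the trial falls short of its stated power for this reason. The documents support none of these.

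Second, the benefit depends on two quantities the documents do not give, rho and a center-level ICC; the 0.01 in C.6 is for classes. This also stands, so it would be too strong to say that adjustment is bound to narrow the intervals.

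Third, the wording of the contrast points most naturally to the week-17 arm difference, so the comparison with change scores concerns the less likely reading. That is fair. The ambiguity is secondary, but one clause would remove it.

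Fourth, complete data is a limiting case: C.6 allows 10% dropout and C.15 plans imputation, which could draw on baseline values. That qualifies the statement that baseline adds nothing to the week-17 contrast. It does not replace adjustment among children with both measurements.

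**Conclusion.** The point holds as a low-cost improvement in precision, not as an error. For child MVPA, diet, screen time and the caregiver outcomes, C.15 names no own-baseline adjustment, although the pre-randomization values will exist. For child BMI z-score and overweight/obesity the gap is smaller, because baseline weight status is listed.

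The size is conditional. At an assumed ICC of 0.01 (class or center level) and any cluster-level correlation from 0 to 1, adjusted variance is 0.835–0.942, 0.660–0.840 and 0.435–0.686 of the week-17 variance at rho 0.3, 0.5 and 0.7. The average gain is assured only for a center ICC below about 0.044, is negligible close to that value, and can become a loss above it. A single six-center trial may not show it. Confidence is medium, because the text is clear but rho and the center ICC are unknown.

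**What to change.** In C.15:
- State whether the effect estimate is the week-17 arm difference or the group-by-time term.
- For each continuous outcome, pre-specify as primary the week-17 value regressed on group, that outcome's own baseline value and the named covariates, with center and class random effects. An equivalent choice is a repeated-measures model with a common baseline mean (no group main effect) and child and center-by-time random effects.
- Keep the group-by-time contrast as a sensitivity analysis, since it can be the more precise one if center ICCs exceed about 0.04 and center effects are stable over time.
- Standardize Cohen's d by the unadjusted SD, and say so, so that the adjustment does not inflate it.

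The cost is plan wording only; C.14 already schedules the measurements. There are two downsides. Children without a baseline value need imputation or the common-baseline model, and the gain depends on a low center ICC.
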